## 4 STATISTICS AND METHODOLOGY

### 4.1. Statistical analysis plan and sample size calculation

Hypothesis 1: Four sessions of motivational interviewing for newly admitted acute patients (within the first 7 days of hospitalization) improve the therapeutic alliance and the adherence for treatment compared to supportive counseling.

Statistical analysis for hypothesis 1: To apply the statistically most sensitive test, we will use an ANCOVA to analyze the treatment effect of motivational interviewing compared to supportive counseling, with baseline values used as covariates.

Hypothesis 2: Four sessions of motivational interviewing for newly admitted acute patients decreases symptom severity compared to supportive counseling.

Statistical analysis for hypothesis 2: We will use an ANCOVA to analyze the treatment effect of motivational interviewing compared to supportive counseling, with baseline values used as covariates.

Hypothesis 3: Patients show higher motivation to seek psychotherapeutic treatment and have a higher self-efficacy expectation after leaving the inpatient stay, when they received an intervention with motivational interviewing compared to supportive counseling.

Statistical analysis for hypothesis 3: We will use an ANCOVA to analyze the treatment effect of motivational interviewing compared to supportive counseling, with baseline values used as covariates.

Additional calculations: We also want to investigate how the number of hospitalization days and the severity of symptoms at the beginning of the intervention have an influence on the therapy outcome. We calculate this with a multiple regression with days of hospitalization and/or the PANSS total score as independent variables. The treatment outcome is defined as the delta between symptoms before and after the intervention and serves as dependent variable.

General statistical considerations: We will use routine procedures of data processing and use data transformation if necessary (in case of non-normal distribution). Standard statistical calculations will be computed. The level of significance will be set to  $p < 0.05$  (two tailed). Effect sizes will be calculated for significant results. The IBM® SPSS Statistics® statistical software as well as the program R will be used.

Sample size justification: Comparable studies found effect sizes that were moderate (Cohen's  $d = 0.3 - 0.5$ ). An effect sizes of  $f = 0.25$  will require us to recruit at least 64 patients per group to achieve 80% power and to detect such an effect with reasonable certainty at an alpha level of 0.05. We therefore plan to include a minimum of  $N = 128$  patients (calculated with G\*Power 3.1).

Analysis population: There is only one analysis population for all hypothesis. For inclusion criteria see chapter 4.1.

Analysis of gender differences: Analyses of gender differences are not planned because there is no research evidence to suggest that gender may be a determining variable. However, it is planned to conduct a group comparison between patients who benefit strongly from MI and those who benefit little, and to investigate possible discriminatory factors as part of this.

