### *Expected relevance*

Therapeutic alliance during the acute phase of psychotic illness is one of the most pressing obstacles for successful long term recovery (e.g. Cavelti et al., 2016). In order for patients to accept much-needed medication and psychosocial therapy and not drop out prematurely, intrinsic motivation to adhere to therapy is crucial. Motivational Interviewing is a method, that has been developed and evaluated over the last three decades and that shows promising results, not only for patients with addiction but also for other patients who struggle with compliance and ambivalence towards treatment and change of behavior. For further information on the method see chapter 3.4. *Study intervention*.

At the same time, it is well known from clinical experience that patients are offered psychotherapy only late during the course of hospitalizations and not when it is most needed – during the acute phase of their illness. Accordingly, there is a clear gap in the literature as to which interventions are particularly useful in this challenging yet crucial phase of the illness.

We believe that the current project and the psychotherapeutic interventions tested here, can provide valuable data on acceptance, feasibility and effectiveness of such interventions and which can then be used to supplement a large multicentre trial across Switzerland.

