## 2.3 Study design

This will be an interventional study with randomized control and open label trial. A parallel-group design with pre- and post-measurements (longitudinal design) will be employed, using subjective and objective measurements with questionnaires and structured interviews. It is a single center and national project.

The study consists of five phases:

1. Screening: Screening will be conducted by the applicant and master's students enrolled in the project who are bound to medical confidentiality, using electronic patient files at the hospital. The patients will be invited to the study by their treating physician or psychologist.

2. Pre-interventional measurement (1 session within the first week, max. 60minutes):

First, the psychopathological symptoms are to be assessed in order to decide about inclusion or exclusion (with PANSS; see also inclusion criteria). In addition, the therapeutic alliance and motivation for psychotherapy are measured. In order to record moderating effects or covariables, demographics (e.g. age, gender, education, years of illness) and two additional questionnaires will be added (attitude towards recovery and the individual motives).

3. Intervention (4 sessions within two weeks, 25- 40 minutes/session):

The patients receive either four sessions of motivational interviewing (intervention group) or four sessions of supportive counseling (control group). For Details see 2.4 "Study intervention"

4. Post-interventional measurement (1 session, max. 60 minutes): At the end of the intervention the motives, the negative symptoms, the hope for recovery, well-being and the level of functioning will be measured again.

The risk of bias should be kept at a minimum. Various precautions are being taken to this end.

- The most important confounding variables are controlled to prevent a bias.
- In order to avoid selection bias, patients are randomly assigned either to the intervention group or to the control group. Randomization is carried out at a 1:1 ratio, using pre-defined random lists (using the online randomization generator: <http://www.pub-med.de/tools/zufallsgenerator>) and a block schema prepared by the principal investigator.
- Block randomization ensures that the patients are distributed in the desired proportion to the two treatment modalities. All patients are randomized only once during the entire examination period.

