#### Expected biases to the study

There are several risks for biases as already described in chapter 2.3 *Study design*. With regard to the method, it must be noted that the effect of psychotherapy is multifactorial and thus difficult to control whether any effects are only due to the difference of the specific method (MI) compared to supportive talks (as a control intervention). In order to control for other possible influencing factors, the level of training of the therapists will be included and controlled for. The degree of motivation for psychotherapy of the patients before the beginning of the intervention as well as the attitude towards recovery on the therapist's side can also influence the outcome of a psychotherapeutic intervention, independent of the method. These specific variables will also be included in our calculations. In addition, it is possible that expectation or attitude toward one of the two therapy methods may have an effect on the outcomes. We will therefore blind the study so that patients do not know which group they belong to ("single-blind").

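### The exploratory regression in section 4.1 has no arm or arm-by-predictor term, so it can show whose symptoms change more but not whether hospital days or starting severity alter the effect of MI

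*Combined protocol and SAP*

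**What the plan says.** Under the additional calculations in section 4.1, the sponsor wants to know how the number of hospital days and the "severity of symptoms at the beginning of the intervention have an influence on the therapy outcome". The method follows: "We calculate this with a multiple regression with days of hospitalization and/or the PANSS total score as independent variables". The outcome is then defined: "The treatment outcome is defined as the delta between symptoms before and after the intervention and serves as dependent variable".

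Other parts of the plan bear on how this is read:

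- Section 2.3 randomises 1:1 to four sessions of MI or four of supportive counselling.
- Section 4.1 states that "There is only one analysis population for all hypothesis". No sentence limits the regression to one arm.
- The confirmatory models do contain arm. For hypothesis 1, "we will use an ANCOVA to analyze the treatment effect of motivational interviewing compared to supportive counseling, with baseline values used as covariates"; hypotheses 2 and 3 use the same model. Arm enters as a main effect only.
- Section 3.3, on expected biases, names therapist training, the patient's motivation before the intervention and the therapist's attitude to recovery, and says of the last two: "These specific variables will also be included in our calculations". Neither arm nor an interaction is among them.
- Section 4.1 also plans to compare patients who gain much from MI with those who gain little. No control-arm contrast is described there.

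**The concern.** Newly admitted inpatients on standard care may recover at a pace that depends on how long they have been in hospital or how ill they were at the start, whichever kind of conversation they receive. A regression of symptom change on those predictors, without arm, picks up that shared pattern. If its slope is reported as an influence on the outcome of the therapy, readers may take it to mean that MI works better for some patients than for others. The model holds no information on that.

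The reverse can also happen. If a predictor goes with better change in one arm and worse change in the other, the slopes offset each other and the pooled analysis shows little. What is at stake is the interpretation of one exploratory result, not the trial's main conclusions.

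**Working it through.** **1. The plan's own figure.** Section 4.1 gives f = 0.25, two-sided alpha 0.05, 80% power and 64 per group. The noncentrality is f² × N = 0.0625 × 128 = 8, and the noncentral F with 1 and 126 degrees of freedom gives power 0.801. The figure reproduces. It concerns the two-group comparison; the documents give no figure for the additional regression.

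**2. What the slope estimates.** Let z be a predictor unrelated to baseline, with slope g(MI) in the MI arm and g(SC) in the control arm. With 1:1 allocation and no arm term:

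- pooled slope = [g(MI) + g(SC)] / 2
- modification of the MI effect = g(MI) − g(SC)

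The average says nothing about the difference. Adding arm as a main effect alone would not change this. A run in the MI arm alone would give g(MI), again without a contrast.

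**3. Simulation for hospital days.** There were 4000 trials per setting, 64 per arm, two-sided 0.05. Assumptions not in the documents: baseline-to-post correlation 0.5; hospital day unrelated to baseline PANSS; in the first four rows, MI effect 0 or 0.5 SD and no modification. Entries are the percentage of trials with a significant term.

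| Setting | Pooled slope of days, PANSS also entered | Pooled slope of days, days only | Arm × days |
|---|---|---|---|
| Correlation with baseline-adjusted recovery 0, both arms | 4.3–4.7 | 4.5–4.6 | 5.0–5.3 |
| Correlation 0.1, both arms | 20–21 | 16–17 | 5 |
| Correlation 0.2, both arms | 59–62 | 49 | 5 |
| Correlation 0.3, both arms | 91–93 | 83–84 | 5 |
| Opposite slopes, 0.2 SD per SD | 6 | – | 71 |
| Opposite slopes, 0.3 SD per SD | 7 | – | 96 |

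Hand check of the 0.2 row with no MI effect: t ≈ 0.2/√(1 − 0.04) × √125 = 2.28, against a critical value of about 1.98, so power ≈ Φ(0.30) = 62%.

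If only the MI arm has a slope g, the pooled slope is g/2 with standard error σ/√N, and the interaction is g with standard error 2σ/√N. The ratios are equal, so power is about the same (24% and 25% at 0.2 SD per SD).

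**4. Starting severity.** Baseline PANSS is part of the delta. If post-treatment PANSS has slope b on baseline, the delta (baseline minus post) has slope 1 − b. For b = 0.3, 0.5 and 0.7 this gives 0.70, 0.50 and 0.30. In simulation the slope was significant in 98–100% of trials, with or without an MI effect and with or without modification of 0.5 SD per SD. The interaction term was significant in about 5% without modification and in 82%, 88% and 96% with it.

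**5. Precision of the interaction.** With residual SD 1, the standard error is 2/√128 = 0.177 SD per SD, so the 95% interval extends about 1.96 × 0.177 = 0.35 either way. For a modification of 0.25 SD per SD, 0.25/0.177 = 1.41 and power ≈ Φ(1.41 − 1.96) = 29%.

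**6. Coding.** With arm coded 0/1 in an interaction model, the coefficient of days is the control-arm slope only, and its standard error rises by √2. For the 0.2 row, 2.28/√2 = 1.61 and power ≈ Φ(1.61 − 1.98) = 36%; simulation gave 36–37%, against about 60% with arm coded −0.5/+0.5.

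**The case against.** The strongest reply is that the plan never asks about effect modification. It defines the outcome as the symptom delta, and on that definition the regression answers its literal question: do hospital days and starting severity predict symptom change? Where section 2.3 mentions moderating effects, it attaches them to demographics and two questionnaires, not to hospital days or PANSS. This stands, and it limits the point to any inference about the effect of the therapy.

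Four stronger readings are tempting, and the documents do not support them:

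- **That the percentages above are false-positive rates of the plan.** They are power to detect a prognostic association that the simulation put in. They become errors only if the slope is read as an effect on what MI achieves. The documents give no prognostic strength and no reason to expect opposite slopes.
- **That the plan states that the arms are pooled.** Pooling is inferred from the absence of any restriction. The sentence on one analysis population refers to the hypotheses, and this is an additional calculation.
- **That timing in the stay, or severity, is the gap the trial sets out to fill.** The section on expected relevance says "there is a clear gap in the literature as to which interventions are particularly useful in this challenging yet crucial phase of the illness". That concerns which interventions help in the acute phase, which the randomised comparisons address. No objective in section 2.1 concerns timing or severity as a modifier.
- **That the main results are compromised.** No hypothesis, endpoint or sample size rests on this regression.

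It is also true that a one-line label would prevent misreading. That would be enough if only prognosis is wanted, but it leaves the randomised comparison unused for data that will be in hand anyway.

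**Conclusion.** The point holds as a cheap improvement to an exploratory analysis. As written, the regression can identify patients whose symptoms change more. It cannot show whether hospital days or starting severity alter the effect of MI against supportive counselling, although the plan describes its target as an influence on the therapy outcome. This follows from the model's terms and needs no simulation. It holds whether the arms are pooled or only the MI arm is used, and no other planned analysis supplies the missing contrast.

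How far the two questions diverge depends on assumptions. With no prognostic association for hospital days, both tests reject in about 5% of trials. With a common correlation of 0.2, the pooled slope is significant in about 60% and the interaction in about 5%. For starting severity the pooled slope is almost always significant, because baseline PANSS is built into the delta.

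**What to change.** In section 4.1, replace the additional regression by the hypothesis 2 ANCOVA with three more terms:

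post PANSS = baseline PANSS + arm + hospital day at start of the intervention + arm × hospital day + arm × baseline PANSS

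- Code arm −0.5/+0.5 and centre both predictors at their means, so that their coefficients are averages over the two arms.
- Report the two interaction estimates with 95% confidence intervals as the exploratory answer on modification of the MI effect.
- Report the arm-averaged slopes of hospital day and baseline PANSS as prognostic only.
- Fix hospital day as the count at the start of the intervention. Section 4.1 does not say whether days run to that point or over the whole stay, and the whole stay extends past randomisation.

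This also settles the open choice between one predictor and both. Using post PANSS instead of the delta loses nothing: with baseline in the model, the arm, day and interaction coefficients are the same apart from sign.

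The cost is one rewritten paragraph. The inputs are already planned (PANSS before and after, hospital days, visit dates), and no extra patients are needed. The drawback is precision: at N = 128 the interaction intervals will be wide and often inconclusive, so the result must stay exploratory.

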### **2.2 Primary and secondary endpoints**

Primary endpoints are the therapeutic alliance as assessed with the *Scale to Assess Therapeutic Relationship STAR* (McGuire-Snieckus et al., 2007) and adherence to treatment as measured with the *Brief Adherence Rating Scale BARS* (Byerly et al., 2008). These variables will be measured before and after the study intervention or control intervention.

Secondary endpoints include changes in symptom severity as assessed with the *Positive and*

*Negative Symptom Scale PANSS* (Kay et al., 1987), as well as the motivation for psychotherapy (measured with the German version of the *Questionnaire to measure the motivation for psychotherapy* by Schulz et al., 1995) and self-efficacy (measured with the *General Self-Efficacy Scale* by Schwarzer & Jerusalem, 1995). All secondary variables will be measured before and after the study intervention or control intervention.

As this study (risk category A) does not include drugs or other medical products and patients are hardly exposed to any more risks than in routine clinical care, no safety endpoints are defined.

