**3.3 Study procedures**

[figure not shown]
Time schedule

The study will last from October 2022 to September 2023.

- From October to December 2022, the study will be planned, and the ethics application will be written and submitted.
- From January, the concrete preparations will take place and
- from February 2023, the implementation will take place. The survey phase will last until August 2023.
- From August to October 2023, the study is to be evaluated, completed and the data analysed.

As can be seen in Table 2, the duration for each patient is between 13 and max. 16 days during their inpatient stay. The goal is to start with the study intervention as soon as possible after entering the psychiatric hospital.

Table 1: Study Flow Chart

**Table 2:** Overview study procedure

\* If questions / need for feedback occur after the last visit, an additional visit shall be provided

	Re-cruitment	Pre-Measurement	Intervention phase				Post-Measurement	
Visits	1 max. 30min.	2 max. 60min.	3 25- 40min .	4 25- 40min .	5 25- 40min .	6 25- 40min .	7 max. 60min.	Follow up max. 60min.
Time (days)	-3 +/-2d	0	2 +/-1d	4 +/-1d	6 +/-1d	8 +/-1d	10 +/-1d	60 +/-5d
Check with treating physician or psychologist	x							
Patient Information and Informed Consent	x							
Randomization	x							
Demographics and information about current treatment	x							
Examination of symptoms with PANSS and MATRICS		x					x	x
Control of In- and Exclusion Criteria		x						
Measurements of secondary outcome variables		x					x	
MI-Intervention (intervention group) or supportive conversations (controls)			x	x	x	x		
Possibility for patients to ask questions and give a feedback							x*	

Detailed description of the planned intervention

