#### Psychometric tests used in the study

Primary diagnosis at point of admittance and medical history are assessed by physicians and psychologists at PUK and documented electronically. The applicant and master's students enrolled in the project will use this available data and document them in specific study protocols. These assessments are part of standard assessments at the hospital by physicians and psychologists. For primary psychiatric diagnoses the International Classification of Diseases (ICD-10) is used.

- Psychotic symptoms are assessed with the *Positive and Negative Syndrome Scale* (PANSS). This is a structured interview, which consists of four scales measuring positive and negative syndromes of schizophrenia, their differential, and general severity of illness.
- Two cognitive tests: Letter-Number-Span (LNS), Symbol-Coding-Test (SCT) from MATRICS (Measurement and Treatment Research to Improve Cognition in Schizophrenia, Consensus Cognitive Battery; Nuechterlein et al., 2008)
- The *Brief Adherence Rating Scale* BARS (Byerly et al, 2008) is a brief, pencil-paper, clinician-administered adherence assessment instrument. It consists of 4 items: 3 questions and an overall visual analog rating scale to assess the proportion of doses taken by the patient in the past month (0%–100%).
- The therapeutic relationship will be evaluated with the *Scale to Assess Therapeutic Relationship* STAR (McGuire-Snieckus et al., 2007). The patient (STAR-P) and clinician scales (STAR-C) each have 12 items comprising three subscales: positive collaboration and positive clinician input in both versions, non-supportive clinician input in the patient version, and emotional difficulties in the clinician version.
- Motivation for psychotherapy will be measured with the *Fragebogen zur Erfassung der Psychotherapiemotivation* (FPTM; engl: "Questionnaire to measure the motivation for psychotherapy") by Schulz, Nübling und Rüdell (1995), a 4-point Likert-scale with 39 items.
- Self-efficacy is measured with the German version of the *General Self-Efficacy Scale* (GSE) by Schwarzer & Jerusalem (1995), an instrument that has been proved with a sample of more than 19'000 persons in 25 countries and shows good psychometric properties.

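### Additional regression in section 4.1: when PANSS total is a predictor of the before-after symptom delta, a slope different from zero is not evidence that severity influences therapy outcome

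*Combined protocol and SAP*

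**What the plan says.** Under Additional calculations, section 4.1 asks how the number of hospital days and the "severity of symptoms at the beginning of the intervention have an influence on the therapy outcome". The method is a multiple regression "with days of hospitalization and/or the PANSS total score as independent variables". The dependent variable is a change score: "The treatment outcome is defined as the delta between symptoms before and after the intervention and serves as dependent variable". No treatment-arm term, interaction or null value other than zero is named.

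The General statistical considerations in the same section set a two-tailed 0.05 level for all tests and add: "Effect sizes will be calculated for significant results".

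Three places bear on what symptoms means. Section 2.2 reads "Secondary endpoints include changes in symptom severity as assessed with the" PANSS. The list of psychometric tests in section 3.3 describes the PANSS: "This is a structured interview, which consists of four scales measuring positive and negative syndromes of schizophrenia". Table 2 schedules "Examination of symptoms with PANSS and MATRICS" at the pre-measurement, the post-measurement and the follow-up. Against these, section 2.3 names only the negative symptoms among the symptom measures repeated after the intervention.

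The paragraph on gender differences in section 4.1 also plans "a group comparison between patients who benefit strongly from MI and those who benefit little".

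**The concern.** The delta is baseline minus post score, so a positive value means improvement. If baseline PANSS is then a predictor, the same measurement stands on both sides of the equation. A patient whose baseline score is too high by chance has a high predictor value and, through the same error, a large apparent improvement. The slope is pushed above zero even if severity has no bearing on outcome.

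Under the plan's rules, such a slope could be declared significant, given an effect size and reported as an influence of severity on therapy outcome. Sections 1 and 6.2 say that the results will inform larger trials, so a statement that sicker patients benefit more could affect whom those trials target.

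**Working it through.** **The plan's own figure.** Section 4.1 gives f = 0.25, 80% power, alpha 0.05 and 64 per group. For two equal groups d = 2f = 0.5. The normal approximation gives 2 × (1.960 + 0.842)² / 0.5² = 62.8, so 63 per arm. The noncentral t gives power 0.795 at 63 and 0.8015 at 64 per arm; with one covariate it is 0.8014 at 64. N = 128 is reproduced and is used below.

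**Algebra.** In general the slope of (pre − post) on pre is 1 − r × (SDpost / SDpre), with r the pre-post correlation. To isolate the artefact, let true symptoms not change at all and let the PANSS have reliability R, with the observed variance set to 1. Then pre = T + e1 and post = T + e2, where each error has variance 1 − R.
- pre − post = e1 − e2, with variance 2(1 − R).
- Covariance with pre = variance of e1 = 1 − R.
- Slope = 1 − R. Correlation ρ = √((1 − R)/2). Share of delta variance explained = (1 − R)/2.

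**Size.** R is an assumption. The expected t is about ρ/√(1 − ρ²) × √126, against a critical value of 1.979.

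| R | slope | ρ | share explained | expected t | approximate rejection | simulated |
|---|---|---|---|---|---|---|
| 0.80 | 0.20 | 0.316 | 10% | 3.74 | Φ(1.76) = 96% | 96% |
| 0.90 | 0.10 | 0.224 | 5% | 2.58 | Φ(0.60) = 72% | 73% |
| 0.95 | 0.05 | 0.158 | 2.5% | 1.80 | Φ(−0.18) = 43% | 44% |

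The nominal rate is 5%.

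**Sensitivity.**
- The table assumes no MI effect. A uniform MI effect of 0.5 SD with no arm term adds noise, and the rates fall to about 92 / 60 / 29%.
- If true change varies between patients independently of severity (SD 0.5 of the baseline SD), they are 81 / 39 / 16%. With an error-free PANSS the rate is 5.2%.
- If the delta is a subscale and the predictor is the total, coupling is weaker. With error only, assumed subscale reliability 0.8 to 0.9 and true subscale correlation 0.2 to 0.5, rejection is 14–32% for the positive or negative scale and 28–67% for the general scale. For a total-score delta it is 46–90% in the same set-up.

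**Days of hospitalization.** Days are not part of the delta, so nothing couples them to it by construction. If days are unrelated to severity, a days-only model rejects in 4.6–5.6%. If days are related to severity (assumed correlation 0.51, no effect of their own), two things can happen.
- Days-only model: days stand in for the baseline score and pick up regression to the mean. With equal SDs, rejection is 82 / 57 / 39 / 22% at r = 0.5 / 0.7 / 0.8 / 0.9.
- Days with baseline PANSS: if days follow true severity, an error-prone baseline adjusts only in part. Rejection is roughly 41–49% at R = 0.80, 23–29% at 0.90 and about 12% at 0.95, the range reflecting the MI effect assumed (0.5 SD or none). If days relate only to the observed score, it is 4.6–5.7%.

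**Interaction.** The arm-by-baseline term rejected in about 5% of null trials (5.1% at R = 0.80). With delta or post as outcome the test is the same, with the sign reversed when delta is pre − post. Its standard error is about 2√(1 − r²)/√124 with equal SDs. Multiplying by 2.80 (1.96 + 0.84) gives the slope difference needed for 80% power: 0.44 / 0.36 / 0.30 / 0.22 at r = 0.5 / 0.7 / 0.8 / 0.9.

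**The case against.** The strongest reply is that the plan writes no zero-slope null and draws no conclusion about sicker patients. Regressing the delta on baseline is also the same fit as regressing the post score on baseline, with slope b becoming 1 − b. So the fault would lie in a future interpretation, not in the model. It is true that the fit is harmless and that the test against zero is inferred. But a multiple regression under a blanket 0.05 rule, with effect sizes for significant results and no other null, leads directly to that test.

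A second reply is that symptoms need not mean PANSS total, since section 2.3 mentions negative symptoms. This stands as an uncertainty: it lowers the rates but does not bring them to 5%.

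The documents do not support several stronger readings:
- **Quoting rejection rates over a range of pre-post correlations and SD ratios as false-positive rates.** In such models expected change truly depends on baseline, so rejection can be correct detection; with shrinking SD it approaches 100% for that reason. With equal SDs and r equal to the reliability, the observed data look the same as with error only. The slope therefore cannot tell the two apart, and the error-only case has to carry the argument.
- **Treating days as safe, or as flawed in the same way.** Neither holds in general, as shown above.
- **Calling the missing arm term an error.** The plan does not say whether the arms are pooled, and a purely prognostic question does not need an interaction.
- **Calling the comparison of strong and weak MI benefiters an error.** As worded it has no controls, so it cannot separate factors for benefit from MI from factors for general improvement. That limits what it can show.

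**Conclusion.** The point holds for the additional regression when PANSS total is entered, and it is minor. Measurement error alone gives a significant slope in about 96 / 73 / 44% of trials at reliability 0.80 / 0.90 / 0.95, so significance there says nothing reliable about severity and therapy outcome.

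This rests on three things the documents do not state: that symptoms means the PANSS score, that the slope is tested against zero, and the reliability values. The first two are the natural reading of sections 2.2, 3.3 and 4.1. The third affects the size of the inflation; it vanishes only for an error-free scale.

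A reader might infer that the trial's main results are compromised. They are not: hypotheses 1 to 3 are tested as group differences in ANCOVAs with baseline as covariate, and N = 128 does not depend on this regression.

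**What to change.** - State which PANSS score forms the delta, and whether the question is moderation or prognosis. Do not interpret the delta-on-baseline slope against zero.
- Moderation (does severity change the benefit of MI over supportive counseling): fit post PANSS on arm, baseline PANSS and arm × baseline PANSS, and read the answer only from the interaction.
- Prognosis: report the baseline slope for post PANSS with its confidence interval, and do not conclude that sicker patients improve more. Changing the outcome from delta to post score does not cure the problem by itself; what changes is the claim.
- Interpret days of hospitalization with the same caution.
- Describe the comparison of strong and weak MI benefiters as prognostic only, or test candidate factors by arm × factor interactions in both arms.
- Label these analyses exploratory and give confidence intervals.

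The cost is wording: PANSS is already scheduled before and after the intervention. The drawback is low power. At N = 128 the arms' slopes must differ by about 0.22 to 0.44 for 80% power, so a non-significant interaction would not show that severity is irrelevant.
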